Therefore, we believe the Veillonella is safe and likely to provide significant benefits in terms of improved endurance, increased energy, and decreased fatigue. This research study is designed to test that hypothesis. FitBiotics is sponsoring this study to confirm these effects in a broader population. FitBiotics is the first company to develop this type of bacteria as a probiotic, and this will be the largest study testing the safety and efficacy of this probiotic.

Objectives

The purpose of this research study is to:

- Test the safety and effectiveness of the study drug, Veillonella (*Veillonella atypica* FB0054), a next-generation probiotic strain.
- Identify the types of benefits observed in a broad population

Study Supplement

The study supplement here includes one of two doses of Veillonella or placebo. Veillonella contains *Veillonella atypica* FB0054 as the active ingredient with microcrystalline cellulose and hypromellose as excipients. The two doses are 15 billion cfu (high dose) and 7.5 billion cfu (low dose). Placebo capsules contain microcrystalline cellulose and hypromellose. Both Veillonella and placebo are encapsulated in acid-resistant capsules to improve delivery to the large intestine, which participants will take orally at home on a daily basis for four weeks.

Subject Selection

Participants in this study will be healthy adults interested in using Veillonella to reduce fatigue and increase energy. Subjects will be excluded from the study if they have conditions, diseases, or medications that could result in increased likelihood of AEs related to Veillonella use.

Inclusion Criteria

- Male or female adults aged 18 – 65 years.
- Willing and able to provide written informed consent.
- Ability of the participant to comprehend the full nature and purpose of the study including possible risks and side effects.
- Agreement to comply with the protocol and study restrictions.
- Fluent in written and spoken English.
- In good general health as judged by the Investigator based on medical history.
- Willing to maintain daily exercise and diet habits throughout the 8 week study without making major lifestyle changes.
- Ability to use a personal smartphone device and download the Chloe app by People Science

Exclusion Criteria

- Currently pregnant, planning to become pregnant, or lactating during the next 12 weeks

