The publication or presentation of any study results shall comply with all applicable privacy laws, including, but not limited to, the Health Insurance Portability and Accountability Act of 1996. Neither the complete nor any part of the results of the study carried out under this protocol, nor any of the information provided by the sponsor for the purposes of performing the study, will be published or passed on to any third party without the written approval of the Study PI. Any investigator involved with this study is obligated to provide the sponsor with all data derived from the study.

Biostatistical Analysis Plan

Data Source

The source of the data is the results of the questionnaires filled out through the Chloe app as well as the optional fitness tracker data collected over the course of the study.

Analysis Objectives

The goals of this analysis are to identify whether there are statistically significant differences in effects between the placebo and Veillonella groups as well as between the high and low dose Veillonella groups. Furthermore, for any differences that are observed, we would like to understand whether there are any demographic or other participant characteristics that may be associated with benefits or side effects experienced by the participants.

Analysis Sets / Populations / Subgroups

The three groups compared in this study are high dose Veillonella, low dose Veillonella, and placebo.

In addition, we plan to separately analyze results by gender, age, baseline exercise habits, health history, previous probiotic experience, sleep habits, and other lifestyle factors.

For those participants who share fitness tracker data, the fitness tracker data shared through the Chloe app will be analyzed in conjunction with survey data separately from those who did not share fitness tracker data.

Endpoints

The primary endpoints analyzed in this study are:

- Change in reported physical fatigue
- Change in mental / emotional fatigue
- Change in MFI

The secondary endpoints analyzed in this study are:

- Change in reported sleep quality
- Change in frequency of reported physical activity
- Change in intensity of reported physical activity
- Change in reported exercise
- Change in recovery time
- Change in energy level

The exploratory endpoints analyzed in this study are:

- Changes in fitness tracker data
- Change in reported bowel movements
- Change in GSE
- Change in reported mood
- Change in reported digestive health

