- Change in reported general health
- Change in BMI, weight, or waist circumference

Handling of Missing Values

There will likely be missing values related to incomplete or missing surveys. Participants will only be included in the analysis if they completed at least 50% of weekly surveys during each time period: baseline, supplementation, and washout. Values will be binned longitudinally such that each participant included in the analysis has a data point associated with each bin. If there are multiple values associated with a participant in a bin, the mean of those values will be used for the analysis.

Statistical Procedures

The majority of primary and secondary endpoints for this study are questions on the survey which consist of rating scales (generally 1-5 or 1-9). Significant differences between groups for these endpoints will be assessed using an independent T test or Mann-Whitney U test depending on the observed

distribution of the data. For significant changes over time within the same group, a dependent T test will be used.

For differences between groups in terms of primary and secondary endpoints that measure a change in time (e.g. time to recovery in days or hours of sleep), an independent T test or Mann-Whitney U test will be used, depending on the observed distribution of the data. For significant changes over time within the same group, a dependent T test will be used.

To identify demographics associated with any particular response (benefit or side effects), we will use the demographic, health history, and lifestyle information collected in the surveys to build an unsupervised machine learning algorithm (e.g. Random Forest Classifier). If we can build one that effectively classifies the response (AUC > 0.7), we will identify the model's most important features. To confirm that these features are significantly associated with response, we will use an independent T test to assess significant differences between response and non-response.

For all other exploratory endpoints including the optional fitness tracker data, the data type and distribution of that data will determine the statistical analysis used.

Measures to Adjust for Confounders

For all data and endpoints, data can be normalized to the baseline collected values, and change in value at different time points can be compared using the statistical tests described above.

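### The six secondary endpoints are tested for significance exactly as the primaries are, with no gate, order, adjustment or descriptive label, so a nominally significant secondary could be reported as a benefit even if every primary fails.

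*Combined protocol and SAP*

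**What the plan says.** All references are to the Biostatistical Analysis Plan in the combined protocol and SAP, unless stated otherwise.

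- **Endpoints.** After "The primary endpoints analyzed in this study are" come three unranked items: physical fatigue, mental or emotional fatigue, and the MFI. After "The secondary endpoints analyzed in this study are" come six: sleep quality, frequency of physical activity, intensity of physical activity, exercise, recovery time and energy level. Only the third list is called exploratory.
- **Statistical Procedures.** The two upper tiers share one rule. It opens "The majority of primary and secondary endpoints for this study are questions on the survey which consist of rating scales (generally 1-5 or 1-9") and continues "Significant differences between groups for these endpoints will be assessed using an independent T test or Mann-Whitney U test depending on the observed" distribution. The next paragraph joins the tiers again, beginning "For differences between groups in terms of primary and secondary endpoints that measure a change in time", and offers the same two tests.
- **Analysis Objectives.** The aim is to "identify whether there are statistically significant differences in effects between the placebo and Veillonella groups as well as between the high and low dose" groups.
- **Objectives (protocol).** One of the two stated purposes is to "Identify the types of benefits observed in a broad population".

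No section gives a significance level, a multiplicity adjustment, a testing order, a dependence of the secondaries on the primaries, or a statement that secondary results are descriptive.

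**The concern.** In many plans the word secondary signals that results are supportive. Here it changes nothing: both tiers get the same test, and statistical significance is the declared goal for both. Six endpoints, each compared across two or three groups, give 6 to 18 opportunities for a nominal p-value below the threshold.

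What is at stake is a statement such as better sleep or more energy that rests on one unadjusted p-value while the fatigue hypothesis is unsupported. Energy matters most, because the Study Synopsis names it beside fatigue as a target of the product, yet it sits in the secondary list. Controlling error across the three primaries alone would leave these six tests as they are.

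**Working it through.** The documents contain no error rate to reproduce, so this is a calculation under stated assumptions.

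**Inputs from the documents**
- Six secondary endpoints (Endpoints).
- Three arms allocated 4:4:2, high dose, low dose and placebo (Details Study Procedures).
- Contrasts: Veillonella against placebo, and high against low dose (Analysis Objectives). The plan does not say whether the doses are pooled against placebo, so both readings are shown.

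**Assumptions (not in the documents)**
- Two-sided 0.05 per test.
- A common correlation r between the six endpoints; 0.5 is the central value and the range is 0 to 0.8.
- Approximately normal test statistics and no effect on any endpoint. The sample size then drops out and only the allocation ratio matters.

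**Formulas.** With arm means H, L and P on a unit scale and weights 4, 4 and 2:
- Each dose against placebo: Z = (H − P)/√(1/4 + 1/2), and the same for L. The two contrasts correlate at (1/2)/(1/4 + 1/2) = 0.667.
- Pooled against placebo: Z = ((H + L)/2 − P)/√(1/8 + 1/2).
- High against low: Z = (H − L)/√(1/4 + 1/4).
- Either direction: P(at least one |Z| > 1.96). Favouring Veillonella: P(at least one Z > 1.96).

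**Exact checks at r = 0, pooled contrast.** Either direction: 1 − 0.95^6 = 0.265. Favouring Veillonella: 1 − 0.975^6 = 0.141.

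**Simulation (400,000 replicates), chance of at least one false secondary result**

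| Contrasts | Tests | Counted | r = 0 | r = 0.5 | r = 0.8 |
|---|---|---|---|---|---|
| Pooled vs placebo | 6 | favouring Veillonella | 14.0% | 10.4% | 7.0% |
| Each dose vs placebo | 12 | favouring Veillonella | 22.8% | 16.5% | 11.2% |
| Pooled vs placebo | 6 | either direction | 26.4% | 20.7% | 13.9% |
| Each dose vs placebo | 12 | either direction | 41.2% | 32.8% | 22.4% |
| Pooled vs placebo, plus high vs low | 12 | either direction | 45.9% | 37.1% | 25.8% |
| All three pairwise | 18 | either direction | 53.9% | 43.4% | 30.3% |

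The benchmark for the first two rows is 2.5%, the chance that one two-sided 0.05 test errs in Veillonella's favour. For the other rows it is 5%.

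**After adjustment (either direction, same null).** When no endpoint has an effect, Holm's error rate equals that of its first step.

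| Rule | r = 0 | r = 0.5 | r = 0.8 |
|---|---|---|---|
| Holm over 6, pooled vs placebo | 4.9% | 4.1% | 2.8% |
| Holm over 6 separately within each dose | 8.7% | 7.2% | 4.9% |
| Holm over all 12 dose-vs-placebo tests | 4.6% | 3.8% | 2.7% |

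The middle row shows why the contrast must be named: applying Holm within each dose does not hold 5% overall.

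**Not counted.** The within-group paired tests, multiple time bins, choice of test after seeing the distribution, optional normalisation and subgroup analyses can all add chances of a nominal result.

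**The case against.** Four points on the other side deserve weight.

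1. **The largest figures do not measure false benefit claims.** A reader might infer a 21% to 43% chance of a false benefit. Those figures also count results favouring placebo, and the upper one counts high-versus-low differences. The figures that match a benefit claim are 10% pooled and 17% by dose. Nor is the pooled figure several times 5%: it is 1.4 to 2.8 times 5% (7% to 14%). It is about four times the 2.5% that applies in one direction (10.4/2.5 = 4.2). This objection stands.
2. **The plan sets no claim rule.** A reader might infer that the sponsor will announce a secondary as a benefit when the primaries fail. The documents do not say so. They state a broad objective and leave the route open, so the supportable word is could.
3. **Secondaries are often read as supportive, and adjustment costs power.** An endpoint with 80% power at 0.05 has 56% at the first Holm step over six tests: Φ(1.960 + 0.842 − 2.638) = Φ(0.164). The plan gives no power calculation against which to judge that loss. The first part fails, because this plan gives secondaries no supportive label and makes significance the goal. The second part stands, and is why a descriptive label must remain an option.
4. **The root omission covers every tier.** The three primaries also lack a multiplicity rule, so a gate on the primary objective protects nothing until success on it is defined. This is right: the two edits belong together. It does not dispose of the point, since a rule for the primaries alone leaves the secondaries openly tested.

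**Conclusion.** The concern holds. As written, the plan tests six secondary endpoints for significance on the same footing as the primaries, and nothing restrains what may be concluded from them.

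Its size is moderate. The relevant risk is a false secondary finding in Veillonella's favour against placebo: about 10% pooled or 17% by dose, where one test would carry 2.5%. The either-direction figures describe how often an inert product yields any significant secondary difference, not how often it yields a false benefit.

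The absence of any rule is read directly from the text. The percentages rest on an assumed two-sided 0.05 and an assumed correlation, and they cover only the between-group tests, once per endpoint and contrast. The change should be made before the data are analysed; it does not call the design into question.

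**What to change.** Add to Statistical Procedures:

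> Secondary endpoints are reported as between-group estimates with 95% confidence intervals, labelled supportive, and are not called significant. The one exception applies if the primary objective is met under a stated success rule that controls error across the three primary endpoints. In that case the pooled Veillonella versus placebo contrast is tested with Holm across the six secondary endpoints at two-sided 0.05. If each dose is instead compared with placebo, Holm covers all 12 tests. High versus low dose on secondary endpoints is descriptive.

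The primary success rule has to be written at the same time, and the choice between pooled and by-dose comparison fixed in advance.

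**Cost.** SAP wording only: no new data, surveys or participants. Fewer secondaries will be called significant, because the smallest p-value must be at most 0.05/6 = 0.0083, or 0.05/12 = 0.0042 with 12 tests. Every estimate and interval can still be reported, so the objective of describing types of benefit survives.

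**Lighter alternative.** If the sponsor does not want to spend alpha on secondaries, labelling all of them descriptive and dropping the word significant for them is enough.

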- Have a significant acute or chronic coexisting illness, disorder, or condition that contraindicates, in the Principal Investigator's judgment, entry to the study.
- Currently taking immunosuppressive medications.
- Is considered immunosuppressed for any reason.
- Currently taking medications that could impair the integrity of the gut epithelia
- Has symptoms or an illness, disorder, or cognition that impairs the integrity of the gut epithelia.
- Current antibiotic use or planned oral antibiotic use over the course of the study.
- Investigator believes that the participant may be uncooperative and/or noncompliant and should therefore not participate in the study.

Research equity

This research has no direct exclusions related to gender. There are also no direct exclusions related to race or ethnicity.

Vulnerable Populations

Vulnerable populations are not specifically targeted in this research. Racial and ethnic minorities will be included in the participants but are not specifically targeted for inclusion.

Study Procedures

See Figure 1 for details of study procedures.

Recruitment

Participants will be recruited to the study via email and social media. Interested participants will sign up through the online study landing page. Participants will be chosen from the pool of signups based on the

inclusion and exclusion criteria above. There is no maximum number of participants. All those eligible will be invited to participate. However, we estimate up to 1,000 participants will be invited to participate in the study.

Details Study Procedures

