Once participants are invited to the study, they will be sent an email with a link to the Chloe application, which they will download to their mobile device. Chloe will lead them through a detailed description of the study and the informed consent process. At this point, they will also consent to sharing their fitness tracker data, as an option, if they have one. The fitness tracker data will be used to answer sleep questions and other fitness tracker data will be stored for analysis by the FitBiomics team. Once informed consent is obtained, participants will fill out a baseline health and lifestyle survey, where they will also share their mailing address. Once this survey is completed, the participant will be randomized to a high dose Veillonella (15 billion cfu), low dose Veillonella (7.5 billion cfu), or placebo in a 4:4:2 ratio respectively. These capsules will be mailed to the participant during the 2 week baseline period.

Completion of the initial baseline health and habit survey initiates the 2 week baseline period. During this period, participants will fill out daily surveys on sleep, energy, and bowel movements and weekly surveys on other benefits and adverse events (AEs) they have noticed (more details on all surveys can be found in Tables 1 and 2). On the final day of the two week baseline, they will also fill out the Multidimensional Fatigue Inventory (MFI) and General Self-Efficacy (GSE) questionnaires. At this point, participants will begin supplementation. Participants will supplement with one capsule daily for 4 weeks. During the supplementation phase, participants will fill out the same daily and weekly surveys. On the final day of the supplementation period, participants will also fill out the Multidimensional Fatigue Inventory and General Self-Efficacy questionnaires. After supplementation, there will be a two week washout period to monitor patients and to understand the lasting effect of any benefits they experienced. During the washout period, participants will again fill out the same daily and weekly surveys. On the final day of the washout period, there will be two additional surveys: one with some additional questions on changes observed throughout the study and one of open ended questions on the whole study experience.

Figure 1. Study Procedures

[figure not shown]

Table 1. Survey Details

| Survey Name | Survey Details | Number of Questions | Estimated Time to complete | Number of Times Used | Total survey time |

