In addition, there is a question included in the weekly surveys assessing how participants are generally feeling about their life, which they respond to using a rating scale from 1 (pessimistic) to 9 (optimistic). If necessary, we can normalize the weekly survey data using this rating to confirm that participant life and stress outside the study are not affecting how they respond to the surveys.

QC Plans

All analyses will be performed by a study bioinformatician or data scientist. All code used for the analysis will be saved using version control software such as Git in the format of Python notebooks. These notebooks will be reviewed by other study staff for errors and certified that analyses are correct prior to any written or oral reports, presentations, or publications on the results of the study.

Programming Plans

All code for these analyses will be written using Python 3 in Jupyter notebooks. The pandas library will be used for importing the data, manipulating it in a data frame, and exporting it as excel or comma-separated files. The Numpy and Scipy libraries will be used for all statistical analysis and the Sci-Kit Learn library will be used for machine learning analyses. Matplotlib and Seaborn libraries will be used for visualization of the data as graphs and charts.

Investigator Conflict of Interest

Investigators will disclose any conflict of interest.

Any investigator who has a conflict of interest with this study (patent ownership, royalties, or financial gain greater than the minimum allowable by their institution, etc.) must have the conflict reviewed by a properly constituted Conflict of Interest Committee with a Committee-sanctioned conflict management

plan that has been reviewed and approved by the study Sponsor prior to participation in this study. All investigators will follow the conflict of interest policy.

References

3. Gross K, Santiago M, Krieger JM, Hagele AM, Zielinska K, Scheiman J, et al. *Acute Impact of Veillonella atypica FB0054 Supplementation on Exercise Performance and Lactate Changes: A Randomized, Crossover Pilot.* *Nutrients. In Review.*

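### The between-arm test for the primary and secondary endpoints is left to the observed data with no rule, and the form of the T test is not stated although each dose is compared with placebo at 2:1

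*Combined protocol and SAP*

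**What the plan says.** All references are to the combined protocol and SAP.

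- **Test, rating endpoints (Statistical Procedures).** Group differences are assessed with an "independent T test or Mann-Whitney U test depending on the observed" distribution of the data.
- **Test, time endpoints (same section).** The rule is repeated: "an independent T test or Mann-Whitney U test will be used, depending on the observed distribution of the data". The MFI change has no rule of its own; I read it as falling under the rating-scale rule.
- **Comparisons (Analysis Objectives).** Differences are sought "between the placebo and Veillonella groups as well as between the high and low dose Veillonella groups".
- **Allocation (Details Study Procedures).** Participants go to high dose, low dose "or placebo in a 4:4:2 ratio respectively".
- **Size (Recruitment).** There is no target and no maximum, only that "we estimate up to 1,000 participants will be invited to participate in the study".
- **Software (Programming Plans).** "The Numpy and Scipy libraries will be used for all statistical analysis".

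No section gives a normality criterion, a default test, or the timing of the choice relative to unblinding. None says whether the T test pools the variances. No significance level and no standard deviations are given. QC Plans provides for checking the code, but not for fixing the method beforehand.

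**The concern.** Two separate gaps meet in one sentence of the plan.

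**Choice of test.** A T test compares means. Mann-Whitney asks whether values in one arm tend to exceed those in the other. On skewed or coarse ratings they can disagree with neither being miscomputed. If the choice is made endpoint by endpoint once the data are visible, the primary hypothesis itself depends on the data. With no criterion to follow, nothing in the text prevents the more favourable result from being the one reported.

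**Form of the T test.** The pooled version assumes equal variances, and with unequal arms it is sensitive to that assumption. If the smaller arm (placebo) is the more variable, the test rejects too often; if it is the less variable, too seldom. Welch's version has no such dependence. The plan does not say which is meant, and the software default is the sensitive one.

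At stake is the meaning and error rate of every claim of significance on the three primary and six secondary endpoints.

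**Working it through.** The plan gives no alpha, SD or power figure, so there is no figure of its own to reproduce.

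**Inputs**
- Allocation 4:4:2 (documents): each dose v placebo 2:1, high v low 1:1.
- Arms of 400 (active) and 200 (placebo): an assumption, as if all 1,000 invited were randomised and analysed.
- Two-sided 0.05: an assumption.
- Placebo variance v relative to active variance 1: an assumption, shown from 0.5 to 2.
- SciPy's `ttest_ind` default, checked in an installed version: `equal_var=True`, the pooled form.

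**1. Free choice when the arms share one distribution.** Simulated with equal means and variances at 400 v 200 (4,000 runs, Monte Carlo SE about 0.3 points). The pretest column is an assumed rule: Shapiro-Wilk at 0.05 in each arm, then pooled T or Mann-Whitney.

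| Data | Pooled T | Welch | Mann-Whitney | Pretest rule | Smaller p |
|---|---|---|---|---|---|
| Normal | 5.0% | 5.0% | 4.9% | 5.0% | 6.0% |
| Rounded ratings | 5.3% | 5.2% | 5.6% | 5.6% | 6.3% |
| Skewed | 5.3% | 5.1% | 4.8% | 4.8% | 7.1% |

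At 100 v 50 (10,000 runs) the pretest rule gave 5.0-5.5% and the smaller p 5.9-6.5%. Any one test fixed in advance is about nominal.

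**2. Pooled T test with unequal variances, 2:1.** Large-sample size = 2 × [1 − Φ(1.96 × √(V_pooled / V_true))], where
- V_pooled = [(399 + 199v)/598] × (1/400 + 1/200)
- V_true = 1/400 + v/200

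| v | V_pooled | V_true | Ratio | Size |
|---|---|---|---|---|
| 0.5 | 0.006252 | 0.005000 | 1.250 | 2.8% |
| 1 | 0.007500 | 0.007500 | 1.000 | 5.0% |
| 1.5 | 0.008748 | 0.010000 | 0.875 | 6.7% |
| 2 | 0.009996 | 0.012500 | 0.800 | 8.0% |

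Simulations at these ratios agree: 6.5-6.6% at 1.5, 7.9-8.5% at 2, and 2.8-3.1% at 0.5. Welch stayed at 4.6-5.3% in them. Over a wider grid (SD ratios 0.5 to 2, three data shapes, 2:1 and 1:1) Welch ran from 4.2% to 5.7%.

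**3. Mann-Whitney with unequal variances, 2:1, normal data, v = 2.** The test uses the variance (1/12)(1/400 + 1/200) = 0.000625. The true variance is A/400 + B/200, with A = arcsin(1/3)/2π = 0.0541 and B = arcsin(2/3)/2π = 0.1161, which gives 0.000716. Size = 2 × [1 − Φ(1.96 × √(0.000625/0.000716))] = 6.7%. Simulations gave 6.6-7.4%.

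**4. High v low, 1:1.** With equal arm sizes V_pooled = V_true for any v, so the pooled T test stays at 5.0%.

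**5. The two tests ask different questions.** With skewed data, equal means and an SD ratio of 1.25 at 400 v 200, Welch rejects in 5.4% and Mann-Whitney in 20.9%. At 400 v 400 the figures are 5.1% and 26.7%. Mann-Whitney is not faulty here; it is not testing means. The ambiguity over what is tested therefore reaches the 1:1 comparison too.

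**The case against.** **The plan does not say pooled.** A reader might infer that neither candidate test holds its error rate. The documents do not support that: Welch's test is also an independent T test, is available in SciPy, and holds its level. The gap is an unspecified form, with a default that goes the wrong way. This objection stands.

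**If the product affects nobody, the variances are equal.** Randomised arms then share one distribution and each test, fixed in advance, holds its level. Unequal spread needs an effect on spread, or selection through the rule that restricts analysis to those completing half the weekly surveys in each period. Both are possible; Data Management expects benefits to differ between subsets. No SD is given, so neither can be checked. This stands and makes the variance figures conditional.

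**The choice is tied to the distribution, not to the p-value.** A reader might infer that analysts will pick the better result after unblinding. The documents do not say so, and are silent on timing. The 6-7% is the cost of an unrestricted choice, not a forecast. A fixed pretest costs almost nothing, but the plan contains none.

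**Discrete ratings.** A reader might infer that any normality check would reject, leaving only Mann-Whitney. That does not follow: endpoints are changes, values within a bin are averaged, and the MFI has 20 items. Under assumed latent-normal data, Shapiro-Wilk at n = 400 rejected in about 8% of runs for a 20-item MFI change and 44% for a binned 1-9 rating. It rejected in 100% for single-rating changes and binned 1-5 ratings.

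**Combined doses v placebo.** Larger distortions arise at 4:1, but Analysis Sets names three groups and nowhere says that the doses will be combined.

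**Conclusion.** The concern holds in a limited form. Without any assumption about variances, the plan leaves open which quantity is tested, and by which test, for its three primary endpoints. The numerical cost of a free choice is modest: about 6-7% against an assumed 5% when the arms share one distribution.

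The variance problem is separate and conditional. It requires the pooled form, or Mann-Whitney read as a test of location, together with unequal variances. It then affects the dose-v-placebo comparisons in either direction: for the pooled T test about 6.5% and 8% at placebo variance 1.5 and 2 times active, and about 3% at half; for Mann-Whitney about 7% at ratio 2. The T test of high v low is not affected.

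The 0.05 level, the 400 v 200 arms and the variance ratios are all assumptions. Arm sizes matter little here, because the 2:1 ratio drives the variance result. The change should be made because the gap is real and closing it is cheap, not because a large error has been shown.

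**What to change.** In Statistical Procedures, name one primary between-arm method for all primary and secondary rating and time endpoints, and date that decision before unblinding.

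- **Preferred:** the difference between arms adjusted for the participant's baseline value, with heteroscedasticity-robust standard errors.
- **Minimum:** Welch's T test on the change from baseline (`equal_var=False`).
- **Mann-Whitney:** reported as a labelled sensitivity analysis that cannot replace the primary result.

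State the significance level and its sidedness in the same place, since the error rate cannot be defined without them.

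Cost: no new data and no added burden on participants. Welch needs SAP wording and one code argument, and loses almost no power at these sizes. The baseline-adjusted version needs a regression library beyond the NumPy and SciPy named in Programming Plans, or a few lines of code, so that section would need a matching edit.
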